REPRISE III: REpositionable Percutaneous Replacement of Stenotic Aortic Valve through Implantation of Lotus™ Valve System – Randomized Clinical Evaluation	
	
study performed will be used for analysis.
 
Note 4: For subjects diagnosed with a neurological event (e.g., stroke, transient ischemic attack), a neurological physical exam (conducted by a neurologist, neurology fellow, neurology physician assistant, or neurology nurse practitioner), NIHSS assessment, and mRS must be performed after the event; mRS must also be administered 90±14 days post-neurological event.
 
a: Kappetein AP, et al. J Am Coll Cardiol. 2012;60:1438
 
b: Leon M, et al. J Am Coll Cardiol. 2011;57:253

Follow-up Schedule	All subjects implanted with a test or control device will be assessed at baseline, peri- and post-procedure, at discharge or 7 days post-procedure (whichever comes first), 30 days, 6 months, 1 year, and then annually for up to 5 years post-procedure. Subjects who are enrolled but not implanted with a test or control device at the time of the procedure will be followed for safety through 1 year.
Study Duration	Subjects implanted with a test or control device will be followed for 5 years after the procedure.

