## 7. Endpoints

Outcomes will be assessed on an intention-to-treat (ITT) basis, an implanted basis, and an as-treated basis. The ITT analysis population of the randomized cohort includes subjects who sign an Informed Consent Form (see Section 0), are enrolled in the trial (see Section 10.1 for point of enrollment), and are randomized, whether or not an assigned study device is implanted. The implanted analysis population includes ITT subjects who are implanted with an assigned, randomized study device. The as-treated population includes subjects who sign an Informed Consent Form, are enrolled in the trial, are randomized, and received a study device, with the analysis based on the treatment actually received. For all analysis sets, if a subject receives 2 valves, the subject is assigned to the group corresponding to the first valve received. Among the roll-in (initial cohort with 23 mm, 25 mm, and 27 mm Lotus Valve System and subsequent cohort with 29 mm LOTUS Edge Valve System), Lotus 21 mm Nested Registry, LOTUS Edge Nested Registry, LOTUS Edge 29 mm Nested Registry, and U.S. Continued Access Study cohorts, for ITT analyses, all subjects who sign the IRB/IEC-approved study ICF and are enrolled in the trial will be included in the analysis sample, regardless of whether the study device was implanted. For these cohorts, the as-treated population includes all subjects implanted with the Lotus/LOTUS Edge valve. Endpoint definitions can be found in Table 26.2-1.

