### **11.11. Study Completion**

All subjects who receive a test or control device will be evaluated at 30 days, 6 months, 12 months, 24 months, 36 months, 48 months, and 60 months post index procedure. All visits are office visits. A subject's participation in the study will be considered complete after the 60-month visit. For subjects who do not receive a test or control device, participation in the study will be considered complete after the 1-year visit.

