### 12.2.1. Analysis Sets

The primary endpoints and additional measurements will be analyzed on an ITT, an as-treated, and an implanted basis. Among the randomized cohort, for ITT analyses, all subjects who sign the IRB/IEC-approved study ICF (see Section 11.3), are enrolled in the trial, and are randomized will be included in the analysis, whether or not an assigned study valve (Lotus Valve or CoreValve) was implanted. The as-treated population includes all subjects who sign the IRB/IEC-approved study ICF, are enrolled in the trial, and are randomized, with the analysis based on the treatment actually received (for example, if a subject is assigned to receive a test device but instead receives a control device, that subject will be considered a control subject for the as-treated analyses). For implanted analyses, ITT subjects who had the assigned, randomized study valve (Lotus Valve or CoreValve) implanted will be included in the analysis. For all analysis sets, if a subject receives 2 valves, the subject is assigned to the group corresponding to the first valve received. Among the roll-in (with the 23 mm, 25 mm, or 27 mm Lotus Valve), Lotus 21 mm Nested Registry, LOTUS Edge Nested Registry, roll-in with the 29 mm LOTUS Edge Valve, LOTUS Edge 29 mm Nested Registry, and U.S. Continued Access Study cohorts, for ITT analyses, all subjects who sign the IRB/IEC-approved study ICF and are enrolled in the trial will be included in the analysis sample, regardless of whether the study device was implanted. For these cohorts, the as-treated population includes all subjects implanted with the Lotus Valve. The as-treated and implanted analysis sets are the same for these cohorts.

For the randomized cohort, the primary safety endpoint, primary effectiveness endpoint (both hypotheses), and the secondary endpoint will all be analyzed for the ITT, as-treated, and implanted analysis sets. The primary analysis for the primary hypothesis of the primary effectiveness endpoint and the primary safety endpoint will be based on the implanted analysis set. The primary analysis set for the secondary hypothesis of the primary effectiveness endpoint and the secondary endpoint will be based on the ITT analysis set.

After 1 year, all analyses will be based on the safety analysis set. All subjects who sign the written ICF, are enrolled in the study, and have a study device implanted regardless of the device and treatment assignment will be included in the safety analysis set.

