### **12.2.4. Reporting Events**

For all subjects in the roll-in (with the 23 mm, 25 mm, or 27 mm Lotus Valve), Lotus 21 mm Nested Registry, LOTUS Edge Nested Registry, roll-in with the 29 mm LOTUS Edge Valve, LOTUS Edge 29 mm Nested Registry, and U.S. Continued Access Study cohorts, all events that occur from the start of the index procedure will be reported. For all randomized subjects, events from the time of randomization onward will be reported. For randomized subjects who do not have an attempted procedure, events from the date of randomization to 1 year post-randomization will be reported. For time based clinical events, the cut-off for events for 30-day endpoints will be 30 days, for 6-month endpoints will be 180 days, for 1-year endpoints will be 365 days, and for 2-5 year endpoints will be 365 days times the number of years. For events at discharge or 7 days post-procedure, the cut-off for events will be the earlier of the date of discharge or 7 days post-procedure for each subject.

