**Table 26.2-1: Definitions**

Term	Definition
	categorized as repeat TAVR, valvuloplasty, or surgical AVR. 
 
• Conversion to open surgery
 
• Conversion to open sternotomy during the TAVR procedure secondary to any procedure-related complications.
 
• Unplanned use of CPB
 
• Unplanned use of CPB for hemodynamic support at any time during the TAVR procedure.
 

RESPIRATORY INSUFFICIENCY	Inadequate ventilation or oxygenation
RESPIRATORY FAILURE	The need for ventilatory support for >72 hours associated with an inability to wean from the respirator for any reason.
RIGHT VENTRICULAR INSUFFICIENCY	
 
• Defined as sequelae of right ventricular failure including the following.                             
 
○ Significantly decreased right ventricular systolic and/or diastolic function
 
○ Tricuspid valvular regurgitation secondary to elevated pressure
 
 
 
• Clinical symptoms to include the following.                             
 
○ Hepatic congestion
 
○ Ascites
 
○ Anasarca
 
○ Presence of “hepato-jugular reflux”
 
○ Edema
 
 
 
 Severe right ventricular dysfunction or severe pulmonary hypertension is primary or secondary pulmonary hypertension with PA systolic pressures greater than 2/3 of systemic pressure.
SAFETY ANALYSIS SET	This population includes all subjects in the ITT analysis set who have a study device implanted, regardless of the assigned treatment group.
SERIOUS ADVERSE DEVICE EFFECT Ref: ISO 14155:2011 (SADE)	Adverse device effect that has resulted in any of the consequences characteristic of a serious adverse event

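### After 1 year all analyses use implanted subjects only, so 2- to 5-year mortality and stroke comparisons drop non-implanted randomized subjects and their already collected first-year events

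*Combined protocol and SAP*

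**What the plan says.** Section 12.2.1 sets the rule for later follow-up: "After 1 year, all analyses will be based on the safety analysis set". It goes on to say that consenting, enrolled subjects who "have a study device implanted regardless of the device and treatment assignment will be included in the safety analysis set". Table 26.2-1 defines the same set this way: "This population includes all subjects in the ITT analysis set who have a study device implanted, regardless of the assigned treatment group". Both definitions require an implanted study device. Neither says how the included subjects are divided into comparison groups.

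The general statements have no time limit. Section 7 says: "Outcomes will be assessed on an intention-to-treat (ITT) basis, an implanted basis, and an as-treated basis". Section 12.2.1 opens in the same way for the primary endpoints and the additional measurements, and adds that the powered endpoints "will all be analyzed for the ITT, as-treated, and implanted analysis sets".

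Later outcomes are planned. Section 7.2 collects the additional measurements through 5 years. In Section 12.2.4 the event cut-off "for 2-5 year endpoints will be 365 days times the number of years". Section 12.1.5 plans Kaplan-Meier estimates, with log-rank and Wilcoxon comparisons between treatment groups.

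Follow-up of non-implanted subjects stops early. The Synopsis says that subjects "enrolled but not implanted with a test or control device at the time of the procedure will be followed for safety through 1 year", and Section 11.11 agrees: "For subjects who do not receive a test or control device, participation in the study will be considered complete after the 1-year visit".

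**The concern.** Implantation happens after randomization. A comparison limited to implanted subjects conditions on a result that the assigned device or the procedure may influence. The randomized non-implanted subjects are probably few, but they may carry a high early death rate. Their first-year deaths and strokes are collected and count in the 1-year ITT results. Under the post-1-year rule, those events leave the 2- to 5-year cumulative curves.

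Two consequences follow. First, the 1-year point on a long-term curve can differ from the reported 1-year ITT rate for no reason other than the change of analysis set. Second, if non-implantation differs between arms, the long-term difference shifts in favor of the arm with more non-implanted subjects, provided those subjects die at a higher rate. The second possibility is not far-fetched: Section 4.2 presents the ability to retrieve the test device and not implant it as a feature beyond earlier devices.

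**Working it through.** The plan gives no figure for the analyses after 1 year and no expected non-implant rate, so there is nothing to reproduce. The check has two parts: what the text does, and how large the effect could be.

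**Text**

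1. Sections 7 and 12.2.1 (opening) put outcomes and additional measurements on ITT, implanted and as-treated sets, with no end date.
2. Section 12.2.1 (last paragraph) puts every analysis after 1 year on the safety set. No ITT analysis is kept.
3. The Synopsis and Sections 11.11 and 12.2.4 collect events in non-implanted subjects through 1 year.
4. Together, first-year events of non-implanted subjects exist in the database and are used at 1 year, but lie outside the set used for the 2- to 5-year cumulative rates.

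**Size at the 1-year point of the long-term mortality curve**

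For one arm, let *p* be the share not implanted, *m* their one-year mortality and *b* the one-year mortality of implanted subjects.

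- ITT rate = (1 − p)·b + p·m
- Safety-set rate = b
- Shift = p·(m − b)

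The full product p·m would overstate the shift, because excluding subjects also shrinks the denominator.

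Inputs:

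- b = 29/249 = 11.6%, the as-treated 1-year mortality in the REPRISE II full cohort (Table 4.1-4). Using it for both arms is an assumption.
- p, low end = 1/250 = 0.4%, from 250 enrolled and 249 as-treated in REPRISE II. The high end of 4% is an assumption.
- m = 30% to 50%, an assumption.

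| p | m = 30% | m = 50% |
|---|---|---|
| 0.4% | 0.004 × 0.184 = 0.07 points | 0.004 × 0.384 = 0.15 points |
| 1% | 0.01 × 0.184 = 0.18 points | 0.01 × 0.384 = 0.38 points |
| 4% | 0.04 × 0.184 = 0.74 points | 0.04 × 0.384 = 1.5 points |

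Across 912 randomized subjects this is 912 × 0.004 ≈ 4 to 912 × 0.04 ≈ 36 subjects outside the set, and 3.6 × 0.30 ≈ 1 to 36.5 × 0.50 ≈ 18 first-year deaths.

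**Between arms**

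With the same m and b in both arms, the difference shifts by (p_Lotus − p_CoreValve)·(m − b). For a 2-point imbalance this is 0.02 × 0.184 = 0.37 to 0.02 × 0.384 = 0.77 points. With equal p and equal m it is zero.

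**Later years**

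If non-implanted survivors are censored at 1 year, only implanted subjects remain at risk. The shift at year t is then p·(m − b) times the conditional survival of implanted subjects from year 1 to year t. The 1-year figures are therefore upper values.

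**The case against.** The case for leaving the plan alone has several sound parts.

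- **No decision depends on it.** All powered endpoints fall at 30 days or 1 year and keep an ITT analysis. Section 12.1.5 plans no inference on the additional measurements. This stands in full.
- **The switch follows the follow-up design.** Non-implanted subjects leave at 1 year, so a complete ITT analysis to 5 years is impossible with the planned data. This stands, but it explains only the missing later follow-up. It does not require dropping first-year events already recorded.
- **A matching 1-year result exists.** In the Synopsis, Section 7 and Table 26.2-1, the as-treated set is randomized subjects who received a study device, which is close to the safety set. Long-term results can be joined to that 1-year analysis, though not to the ITT one.
- **The Section 7 conflict may be only a general rule with an exception.** That is a fair reading. Even so, Section 7 gives no hint of the exception.
- **Valve outcomes cannot be ITT.** Subjects without an implanted valve need no follow-up echocardiogram (Table 11.1-1, note i). The point therefore covers mortality and stroke only.
- **Censoring at 1 year may be informative.** If non-implanted subjects are high-risk, censoring their survivors assumes a later risk that they may not have. This stands as a limitation of the fix.
- **The rate may be tiny.** REPRISE II suggests 0.4%. The one larger figure, 1 of 7 without a valve in REPRISE NG DS Cohort B (Section 4.1.4), is too small to set a rate. No CoreValve rate is given.

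A reader might also infer that the plan abandons the randomized comparison and regroups subjects by device received. The documents do not say that. Ignoring assignment is stated as a rule for entry into the set. Exclusion of non-implanted subjects is certain; regrouping is only possible, because the grouping rule is missing.

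**Conclusion.** The point holds for 2- to 5-year time-to-event outcomes, chiefly mortality and stroke, in the randomized cohort. As written, those comparisons condition on implantation and omit collected first-year events. They also sit awkwardly with the unrestricted ITT statements and have no stated grouping rule.

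The likely size is small: about 0.07 to 1.5 percentage points of cumulative mortality per arm, and about 0.4 to 0.8 points on the difference if non-implant rates differ by 2 points. These figures rest on assumed non-implant rates of 0.4% to 4%, assumed mortality of 30% to 50% in those subjects, and 11.6% in implanted subjects of both arms. Equal non-implant rates and equal mortality would give no between-arm bias. The documents support no comparable estimate for stroke.

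It would be wrong to infer that these deaths disappear from the trial's results or that the primary conclusions are at risk. The events count in the 1-year ITT analyses, and every powered endpoint is untouched. This is an inexpensive improvement to the long-term descriptive results.

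**What to change.** For the randomized cohort, amend Section 12.2.1 as follows.

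1. Keep an as-randomized (ITT) Kaplan-Meier analysis of mortality and stroke at 2 to 5 years. Count first-year events in non-implanted subjects and censor their survivors at last contact, about 1 year.
2. Report the safety set alongside it, and state whether subjects are grouped by assigned or received device.
3. Keep valve and echocardiographic outcomes on implanted subjects.
4. Align Section 7, Section 12.2.1 and Table 26.2-1. Add the post-1-year rule to Section 7. Use one safety-set definition: Section 12.2.1 starts from enrolled subjects, while the table starts from the ITT set.
5. State as a limitation that censoring non-implanted survivors at about 1 year may be informative.

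The cost is wording and one more set of tables. No extra visits or data are needed.

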### 12.2.2. Control of Systematic Error/Bias

All subjects who have met the inclusion/exclusion criteria, received a positive recommendation from the CRC, and signed the Informed Consent Form will be eligible for

enrollment in the study. The center heart team's assessment of TTE measurements before device placement will contribute to the determination of subject eligibility for the study.

To control for inter-observer variability, data from independent core laboratories (see Section 13.3) will be used for analysis. These include an echocardiography core lab, a CT and rotational X-ray angiography core laboratory to assess all CT and rotational X-ray data using standard techniques, and an electrocardiography core laboratory to independently analyze protocol-required 12-lead ECGs performed for each subject.

### **12.2.3. Randomization Scheme**

A computer generated list of random treatment allocations (i.e., a randomization schedule) will be used to assign subjects to treatment in a 2:1 ratio of Lotus Valve to CoreValve. Randomization will be stratified by center and risk factor (extreme and high operative risk with a targeted enrollment of at least 30% of subjects in each group; see Table 26.2-1 for operative risk definitions). Additional information is provided in the study Manual of Operations.

### **12.2.4. Reporting Events**

For all subjects in the roll-in (with the 23 mm, 25 mm, or 27 mm Lotus Valve), Lotus 21 mm Nested Registry, LOTUS Edge Nested Registry, roll-in with the 29 mm LOTUS Edge Valve, LOTUS Edge 29 mm Nested Registry, and U.S. Continued Access Study cohorts, all events that occur from the start of the index procedure will be reported. For all randomized subjects, events from the time of randomization onward will be reported. For randomized subjects who do not have an attempted procedure, events from the date of randomization to 1 year post-randomization will be reported. For time based clinical events, the cut-off for events for 30-day endpoints will be 30 days, for 6-month endpoints will be 180 days, for 1-year endpoints will be 365 days, and for 2-5 year endpoints will be 365 days times the number of years. For events at discharge or 7 days post-procedure, the cut-off for events will be the earlier of the date of discharge or 7 days post-procedure for each subject.

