## 7.2. Additional Measurements

Additional measurements based on the VARC endpoints and definitions (see **Note 1** below) will be collected peri- and post-procedure, at discharge or 7 days post-procedure (whichever comes first), 30 days, 6 months, and 1, 2, 3, 4, and 5 years post index procedure, unless otherwise specified below.

- Safety endpoints (see **Note 2** below) adjudicated by an independent Clinical Events Committee (CEC; Section 22.1.1):
  - Mortality: all-cause, cardiovascular, and non-cardiovascular
  - Stroke: disabling and non-disabling
  - Myocardial infarction (MI): periprocedural ( $\leq 72$  hours post index procedure) and spontaneous ( $> 72$  hours post index procedure)
  - Bleeding: life-threatening (or disabling) and major
  - Acute kidney injury ( $\leq 7$  days post index procedure): based on the AKIN System Stage 3 (including renal replacement therapy) or Stage 2
  - Major vascular complication
  - Repeat procedure for valve-related dysfunction (surgical or interventional therapy)
  - Hospitalization for valve-related symptoms or worsening CHF (NYHA class III or IV)
  - New permanent pacemaker implantation resulting from new or worsened conduction disturbances (definitions in Table 26.2-1; see **Note 3** below)
  - New onset of atrial fibrillation or atrial flutter
  - Coronary obstruction: periprocedural ( $\leq 72$  hours post index procedure)
  - Ventricular septal perforation: periprocedural ( $\leq 72$  hours post index procedure)
  - Mitral apparatus damage: periprocedural ( $\leq 72$  hours post index procedure)
  - Cardiac tamponade: periprocedural ( $\leq 72$  hours post index procedure)
  - Prosthetic aortic valve malpositioning, including valve migration, valve embolization, or ectopic valve deployment
  - Transcatheter aortic valve (TAV)-in-TAV deployment

- Prosthetic aortic valve thrombosis
- Prosthetic aortic valve endocarditis
- Device performance endpoints peri- and post-procedure:
  - Successful vascular access, delivery and deployment of the study valve and successful retrieval of the delivery system
  - Successful retrieval of the study valve if retrieval is attempted
  - Successful repositioning of the study valve if repositioning is attempted (see **Note 4** below)

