**Table 11.1-1: Study Event Schedule**

Assessment	Screening a	Baseline	Procedure	Within 1 Day Post-procedure	Prior to Discharge or 7 Days Post-Procedure	30 Days b (±7 Days) Office Visit	6 Months b (±30 Days) Office Visit	12 Months b (±30 Days) Office Visit	24–60 Months b [Annual] (±45 Days) Office Visit
------------	------------------------	----------	-----------	-----------------------------	---	---	---	--	--

Imaging Core Laboratory procedure guidelines (see study Manual of Operations). Results must be forwarded to the CT/X-Ray Core Laboratory for analysis. If additional imaging is performed (e.g., cardiac CT or MRI scan), data may be provided for analysis.

- o: Includes the Kansas City Cardiomyopathy and SF-12 QOL questionnaires. Baseline QOLs should be performed within 30 days prior to the index procedure.
- p: QOL survey at 36 and 60 months.
- q: Procedural cine-angiogram including final post-deployment aortogram of the ascending aorta must be done and sent to the CT/X-Ray Core Laboratory for analysis.
- r: For subjects who received a permanent pacemaker related to the index procedure, pacemaker dependence must be captured at the 30-day and 1-year visits via pacemaker interrogation. Pacemaker interrogation should also include assessment of the percentage of beats where the ventricles are paced.
- s: AEs and ADEs will be monitored and collected from the time of enrollment through 12-month follow-up. For subjects who do not receive the study device, AEs will be monitored through 1-year follow-up.
- t: Information on device deficiencies for the test and the control devices, as well as all SAEs, SADEs, UADEs, USADEs, and CEC events will be monitored and reported to Boston Scientific for all enrolled subjects from the time of enrollment through termination of the study. For subjects who do not receive a study device (test or control), the mentioned events will be monitored through 1 year post-index procedure. Please refer to Section 7.2 for a list of CEC events and Table 26.2-1 for definitions of these events, which specify data required for CEC adjudication. Complaint reporting of any device deficiencies for any commercially available products used should also be carried out using the manufacturer’s processes.

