#### 12.1.1.1. Statistical Hypothesis for the Primary Safety Endpoint

The statistical hypothesis is that the rate of the primary safety endpoint (composite of all-cause mortality, stroke, life-threatening and major bleeding events, stage 2 or 3 acute kidney injury, or major vascular complications at 30 days) for the Lotus Valve is non-inferior to that for CoreValve.

The primary safety endpoint is expressed as the proportion of subjects who experience mortality, stroke, life-threatening and major bleeding events, stage 2 or 3 acute kidney injury, or major vascular complications within 30 days after the index procedure among all subjects who either experience mortality/stroke/life-threatening or major bleeding events/stage 2 or 3 acute kidney injury/major vascular complications within 30 days after the index procedure or are followed for at least 23 days after the index procedure.

The null and alternative hypotheses for the primary safety endpoint are as follows:

$$H_0: P_{S\_Lotus} \text{ minus } P_{S\_Control} \geq \Delta \text{ (Inferior)}$$

$$H_1: P_{S\_Lotus} \text{ minus } P_{S\_Control} < \Delta \text{ (Non-inferior)}$$

where  $P_{S\_Lotus}$  and  $P_{S\_Control}$  are the rates of the primary safety endpoint at 30 days for the Lotus Valve (test) group and the CoreValve group (control), respectively, and  $\Delta$  (delta) is the non-inferiority margin.

A Farrington-Manning standardized test will be used to test the one-sided hypothesis of noninferiority in the difference between the rates of the two treatment groups, as described in the Statistical Analysis Plan. If the  $P$  value from the Farrington-Manning standardized test is  $<0.025$ , the rate of the primary safety endpoint for the Lotus Valve will be concluded to be non-inferior to the CoreValve rate. This corresponds to the one-sided upper 97.5% confidence bound on the difference between treatment groups (Lotus Valve minus CoreValve) for the observed rate of the primary safety endpoint at 1 year being less than the non-inferiority margin.

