#### **12.1.5. Post-procedure Measurements**

Post-procedure information will be collected at regularly scheduled follow-up examinations as detailed in the clinical study schedule (Table 11.1-1) and will be summarized using descriptive statistics for continuous variables (e.g., mean, standard deviation, n, minimum, maximum) and frequency tables or proportions for discrete variables. Estimates will be reported by treatment group and, for randomized subjects, differences between treatment groups and their 95% confidence intervals will be presented. Treatments for the randomized subjects will be compared with the chi-square or Fisher exact test for discrete variables and the Student t-test for continuous variables. No inferences are planned on the additional measurements and, therefore, alpha-adjustments for multiple comparisons will not be used. The Kaplan-Meier product-limit method will be used to estimate rates for time-to-event endpoints and treatment groups will be compared using the Log-rank and Wilcoxon tests. Adverse event and SAE rates will be reported. No formal statistical testing will be done for the roll-in (with the 23 mm, 25 mm, or 27 mm Lotus Valve), Lotus 21 mm Nested Registry, LOTUS Edge Nested Registry, roll-in with the 29 mm LOTUS Edge Valve, LOTUS Edge 29 mm Nested Registry, or U.S. Continued Access Study subjects.

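### Discharge/7-day event rates stop at each subject's own discharge, so between-arm comparisons at that time point can pick up differences in length of stay (low severity, cheap to fix)

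*Combined protocol and SAP*

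**What the plan says.** Section 12.2.4 (Reporting Events) sets the counting windows. Most are fixed: for instance, "the cut-off for events for 30-day endpoints will be 30 days", and the later ones are 180 days, 365 days and multiples of 365 days. The earliest time point is the exception: "the cut-off for events will be the earlier of the date of discharge or 7 days post-procedure for each subject".

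Section 7.2 makes this a reporting time for the additional measurements, which "will be collected peri- and post-procedure, at discharge or 7 days post-procedure (whichever comes first), 30 days" and at later visits. They include stroke, bleeding, major vascular complication and new pacemaker.

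Section 12.1.5 gives the analysis: "Treatments for the randomized subjects will be compared with the chi-square or Fisher exact test for discrete variables", with differences and 95% confidence intervals. It also limits the status of these results: "No inferences are planned on the additional measurements and, therefore, alpha-adjustments for multiple comparisons will not be used". It adds that "The Kaplan-Meier product-limit method will be used to estimate rates for time-to-event endpoints", but does not say whether this covers the discharge/7-day rates.

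Event collection does not stop at discharge. Table 11.1-1, footnote s, states that "AEs and ADEs will be monitored and collected from the time of enrollment through 12-month follow-up". Footnote t carries serious events and centrally adjudicated events further still.

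**The concern.** Discharge happens after randomization and may depend on the device and on what happened during the procedure. A subject who goes home on day 3 and has a stroke on day 5 counts as event-free at this time point. A subject still in hospital with the same day-5 stroke counts as an event. A chi-square or Fisher test on the two proportions treats them as risks over a common period, which they are not.

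If stays differ between arms, the arm that goes home sooner is observed for less time and can look safer for that reason alone. At stake is the reading of the earliest between-arm table for those adverse events that have no fixed early window of their own.

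**Working it through.** **Figures in the plan.** No sample size, power or alpha uses the discharge cut-off, so there is no stated figure to reproduce. As context, the powered analyses were recomputed: safety non-inferiority 85.4% (stated about 85%), effectiveness non-inferiority 80.2% (stated 80%), effectiveness superiority 86.6% (stated about 86%), secondary endpoint 86.4% (stated about 86%). None depends on this window.

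**Inputs.** From the documents: the cut-off min(discharge, day 7) in 12.2.4, and arm sizes of 608 and 304 in 12.1.1.2. Assumed, because the documents give neither length of stay nor event timing:
- the true 7-day risk is 15% in both arms;
- stay L = 1 + Poisson(m − 1) days, with mean m of 3 days in one arm and 3, 4, 5 or 6 in the other;
- event times are independent of stay, and either uniform over days 0–7 or front-loaded (80% within the first day, the rest uniform over days 1–7).

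**Formulas.** Let W be the mean of min(L, 7). For m = 3, 4, 5, 6, W = 2.99, 3.95, 4.80, 5.51 days.
- Uniform: reported rate = 15% × W/7.
- Front-loaded: reported rate = 15% × [0.8 + 0.2 × (W − 1)/6].

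For example, m = 5, uniform: 15% × 4.80/7 = 10.3%. For m = 3, front-loaded: 15% × [0.8 + 0.2 × 1.99/6] = 13.0%.

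| Mean stay (days) | Uniform | Difference (points) | Front-loaded | Difference (points) |
|---|---|---|---|---|
| 3 v 3 | 6.4% v 6.4% | 0 | 13.0% v 13.0% | 0 |
| 4 v 3 | 8.5% v 6.4% | 2.1 | 13.5% v 13.0% | 0.5 |
| 5 v 3 | 10.3% v 6.4% | 3.9 | 13.9% v 13.0% | 0.9 |
| 6 v 3 | 11.8% v 6.4% | 5.4 | 14.3% v 13.0% | 1.3 |

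A simulation with 2,000,000 subjects per arm agrees to within 0.1 point. With a fixed 7-day window it returns 15.0% v 15.0% in every row.

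**Chance of a nominal p < 0.05 against the longer-stay arm**, taking that arm as the one with 608 subjects: Φ((d − 1.96 × SE0)/SE1), where d is the difference and SE0 and SE1 are its standard errors with pooled and separate rates. For 5 v 3 days, uniform, the pooled rate is (608 × 0.103 + 304 × 0.064)/912 = 0.090. SE0 = √(0.090 × 0.910 × (1/608 + 1/304)) = 0.0201. SE1 = √(0.103 × 0.897/608 + 0.064 × 0.936/304) = 0.0187. The result is Φ((0.039 − 0.0394)/0.0187), about 49%. For 4 v 3 and 6 v 3 it is about 18% and 74%. Under front-loading it is about 4 to 7%. With no difference it would be 2.5% in that direction.

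**Sensitivity to timing.** Take fixed stays of 3 v 5 days and exponential onset with mean μ, truncated at day 7. The share of 7-day events counted by day t is F(t) = (1 − e^(−t/μ))/(1 − e^(−7/μ)). Multiplying F(5) − F(3) by 15% gives:
- μ = 0.5: (0.99996 − 0.99752) × 15 = 0.04 points;
- μ = 1.5: (0.9735 − 0.8729) × 15 = 1.5 points;
- μ = 5: (0.8390 − 0.5989) × 15 = 3.6 points.

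So 0.5 points is not a floor. If nearly all events fall on the procedure day, the artefact almost vanishes.

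**The case against.** **The results are descriptive.** No inference is planned on the additional measurements. The primary safety endpoint uses a 30-day window and counts event-free subjects only if they "are followed for at least 23 days after the index procedure". The primary effectiveness and secondary endpoints are at 1 year. A day-5 event after a day-3 discharge still enters the 30-day rate. Several procedural complications have their own 72-hour definitions. All of this stands, and it limits the severity.

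**The time point is openly labelled.** Discharge or day 7, whichever is first, is defined throughout and matches the earlier REPRISE NG DS tables. That is a fair defence of the rate as an in-hospital summary, but not of a between-arm test on it.

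**A longer stay may be a result of complications.** This is true, and the model above ignores it. It does not rescue the rule. If one device leads to more pacemakers and these prolong stay, the longer window also catches more of that arm's later bleeds or strokes, so a real difference in one event spills into others.

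**Kaplan-Meier could handle unequal follow-up.** The plan does not tie it to this time point, and censoring at discharge would probably be informative.

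A reader might infer that the windows do differ by arm, and that the longer-stay arm shows more events by construction. The documents do not support this. The rule is the same in both arms, and no length of stay or discharge criterion is given. A reader might also cite Table 4.1-6, where new pacemakers in NG DS Cohort A go from 0/10 at discharge to 3/10 at 30 days. That single-arm contrast cannot place any of the three before day 7, and Cohort C (Table 4.1-8) shows 2/21 at both times. Stroke in both cohorts, life-threatening bleeding in Cohort A and major vascular complications in Cohort C likewise do not change between discharge and 30 days. These samples are too small to settle the matter either way.

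**Conclusion.** The point holds in a conditional form. The discharge/7-day window depends on a post-randomization variable, and section 12.1.5 plans between-arm tests without allowing for it. A false difference needs two things that the documents neither show nor exclude: stays that differ by arm, and events between discharge and day 7.

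The ranges in the table hold for a 15% true risk, mean-stay gaps of 1 to 3 days and stay independent of events; they are illustrations, not estimates for this trial. It would be wrong to conclude that any powered analysis, the type I error control or the 30-day safety comparison is compromised. Severity is low. The change is worth making because it costs little.

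**What to change.** In section 12.2.4 and the SAP, use a fixed cut-off of 7 days post-procedure, whatever the discharge date, for every between-arm comparison of dated clinical events at this time point. Keep the discharge-truncated rate as a labelled in-hospital descriptive line without a between-arm test, which preserves comparability with the earlier REPRISE tables. Report length of stay by arm; the existing rule already needs each discharge date.

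For most events this takes one sentence and no new data, since dated events are collected after discharge. Acute kidney injury is the exception. Table 11.1-1, footnote f, asks for its assessment only through discharge/7 days, and the schedule lists no routine laboratory tests after the first post-procedure day. A day-7 rate for it would still depend on when subjects went home and should carry a note saying so.

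The downside is one more reported rate, with 7-day figures slightly higher than the discharge-truncated ones.
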